
Transcutaneous Auricular Vagus Nerve Stimulation (taVNS) to Reduce PTSD Symptoms in WTC Responders

Protocol Number: 21-0640

February 1, 2022

PTSD who experience barriers to treatment engagement and adherence.

Protocol Number: 21-0640

February 1, 2022

Objectives:

Aim 1 seeks to conduct a formative phase evaluation in order to ensure that the taVNS intervention and the pilot study methodology are relevant and acceptable for use with WTC responders with PTSD. For the evaluation, we will recruit 10 WTC responders to participate in a focus group.

Aim 2 seeks to conduct a randomized, double-blind placebo-controlled parallel-design pilot study, to determine whether the taVNS intervention and study methodology are feasible and acceptable for use with WTC responders with PTSD. We hypothesize that the taVNS intervention will be feasible and acceptable for this population. We will also use the initial study results to understand signals that point to potential variables to include that best indicate taVNS efficacy, and potential mediators of the impact of taVNS when implemented in a future RCT involving multiple World Trade Center Health Program (WTCHP) sites. Within both the intervention and sham control groups, responders who are in any form of MH treatment will stay in their usual treatment. Information regarding any current or past treatment will be collected.

Protocol Number: 21-0640

February 1, 2022

Endpoints:

The primary endpoint of this study will be the feasibility of the taVNS intervention. This will be measured at the 8-week follow-up. Feasibility will be evaluated as: (1) rates of recruitment (per month), (2) adherence to the taVNS intervention, (3) 8-week retention, and (4) duration and completion rate of study assessments. Feasibility is defined as the ability to recruit 75% of eligible participants who were approached, as well as to show adherence to the intervention and retention rates of 70% each.

The secondary endpoint of this study will be acceptability of the taVNS intervention. This will be measured at the 8-week follow-up. Acceptability will be evaluated by assessing: (1) the time to completion of questionnaires, (2) percentage of missing data from questionnaires, (3) the time to completion of the biological data and blood draw, (4) the rate of refusal of biologic measurements and blood draw, and (5) the score on the taVNS Satisfaction and Usefulness Questionnaire.

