The responder will receive \$20 and transportation costs, \$25, for completion of the CAPS regardless of whether or not he or she is eligible for the pilot study. Based on our previous research,⁹⁷ we expect that of the 477 potential participants, approximately 182 will need to be called in order to reach a 33% screening participation rate, to yield 60 responders who meet the phone screen criteria and agree to come in for the CAPS interview. Of those 60 responders, we expect that 66% (n=40) will meet criteria for PTSD as per the CAPS, and will therefore be eligible for the study based on [name] previous study involving recruitment and enrollment of military Veterans with PTSD.⁹⁸ Based on our prior experience of clinical taVNS studies on both healthy and disease cohorts,³⁷ of those 40, we expect that at least 75% (n=30) will agree to continue with study participation.

In order to increase recruitment, we are working with Mount Sinai WTCHP Data Center to identify additional eligible patients. These participants previously consented to be contacted for research.

This information includes: names, contact information (mailing address, phone numbers and email addresses) for members who scored ≥ 44 on their most recently completed PCL/PTSD checklist since 1/1/2019 who live within a 10 mile radius from the Feinstein Institutes for Medical Research ([name]).

This will be provided to us from Mount Sinai WTCHP Data Center, we will not be giving any information to them.

Even though we have a data use agreement in place, we are requesting a HIPAA waiver of authorization to receive and possess the WTCHP PHI. Providers previously gave permission to be contacted, but in order for us to only reach out to those potentially eligible, we need to know additional information and it isn't feasible to reach out to each participant for this information. All participants are consented prior to any research activity.

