6 STUDY INTERVENTION

6.1 STUDY INTERVENTION(S) ADMINISTRATION

6.1.1 STUDY INTERVENTION DESCRIPTION

Aim 1: A Focus Group Discussion Guide will be finalized by the research team prior to recruitment (see Appendix 1 for example blank focus group data collection instrument). It will include questions to understand the relevance, feasibility and acceptability of: (1) using a taVNS device generally, (2) using it as treatment for PTSD, (3) the implementation protocol of the device, (4) the pilot study protocol (including the methodology details, timing, and both self-report, clinical, and biological assessments), and (5) the appropriateness of outcome measures. The estimated duration for the focus group is \approx 90 minutes. Drs. [name] and [name] will co-lead the focus group and the coordinator will take notes, write the minutes, and audio-record the session. [name] and/or [name] will demonstrate the device. Individuals will have the opportunity to handle the devices and there will be sanitizing wipes to be used in between. The focus group will be transcribed for qualitative analyses.

Aim 2:

Table 1. Aim 2 Outcome Measures	
Primary Outcome Measures (measured at 8 weeks)	
FEASIBILITY	
Recruitment	
-% responders who meet criteria 1-3 who accepted to come in for the CAPS interview (goal=33%)	
-% eligible responders who meet criteria 1-4 of those who came in for the CAPS interview (goal=66%)	
-% eligible responders who meet all criteria and were recruited and consented (goal = 75%)	
Retention	
-% participants who complete baseline and 8-wk measures (both survey and biological measures) (goal = 90%)	
Adherence	
-% participants who used taVNS 15 min/day once a day for 8 weeks (21 hours total) (goal=80%)	
Secondary Outcome Measures (measured at 8 weeks)	
ACCEPTABILITY	
Collection of Measures	
-Time (minutes) to fill out questionnaires (goal =<30 min)	
-Missing data from questionnaires: % items complete on the baseline and 8-wk self-report surveys (goal=90%)	
-Time (minutes) to collect biological data and blood draw (goal=10 min at baseline and 10 minutes at follow-up)	
-Rate of refusal of biologic measurements/blood draw (goal=5% refusal)	
Satisfaction	
-taVNS Intervention Study satisfaction survey (Adapted from Bakken et al.) (range=12-60; goal=100%-with score >47 among intervention group) ¹⁰⁰	
Tertiary Outcome Measures (measured at baseline and 8 week follow-up)	
Mental health symptoms (assessed to indicate signals for hypothesis generation)	

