8 STUDY ASSESSMENTS AND PROCEDURES

8.1 EFFICACY ASSESSMENTS

Aim 2: Primary Outcome Measure: Feasibility will be evaluated using criteria suggested by Leon⁹⁹: 1) rates of recruitment (per month), 2) adherence to the taVNS intervention, 3) 8-week retention, and 4) duration and completion rate of study assessments. Feasibility is defined as the ability to recruit 75% of eligible, approached, participants and to demonstrate intervention adherence and retention rates of 70% each (Table 1). **Secondary Outcome Measure:**

Protocol Number: 21-0640

February 1, 2022

Acceptability will be evaluated by assessing: 1) time to completion of questionnaires, 2) percentage of missing data from questionnaires, 3) time to completion of the biological data and blood draw, 4) rate of refusal of biologic measurements and blood draw, and 5) score on the taVNS Satisfaction and Usefulness Questionnaire¹⁰⁰ (Table 1). **Tertiary Outcome Measures** include potential taVNS endpoint measures. At the baseline and 8 week follow-up visits, validated self-report MH measures, including assessments of PTSD,⁹⁴ anxiety,¹⁰¹ depression,¹⁰² sleep,¹⁰³ and the CAPS interview⁹⁵ (at screener and follow-up) will be administered. To examine **potential mechanisms of action** and any acute and longer-term change in these mechanisms, the biological measures will be administered at baseline 10 minutes before using the device, again one time at the 8-week follow-up visit. Blood will be drawn to assess markers of inflammation before using the device, after using the device, and again at the 8 week follow-up visit. This allows us to collect data to understand potential acute and long-term effects. These tertiary outcome measures and potential mechanisms of action will be used to inform the

design of a future, RCT to evaluate taVNS efficacy. Measurement quality, amount of missingness or non-response, length of measurement collection, and costs will be assessed. These measures will also be used to provide parameter estimates for power calculations for a future RCT (Table 1). We will also use the preliminary efficacy results from this pilot to generate hypotheses regarding potential mechanisms of action including the various inflammatory, neural and cardiovascular changes that correlate with treatment outcomes

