0.80	0.61	0.92	0.31
0.85	0.67	0.95	0.28
0.90	0.74	0.98	0.24
0.95	0.80	1.00	0.19

CL=confidence level

Protocol Number: 21-0640

February 1, 2022

measures are expected to be 75% for recruitment, 90% for retention, and 80% for adherence.

Two-sided 95% confidence intervals for one proportion were calculated using the Clopper-Pearson method, with scenarios varying the expected percent (0.70-0.95), in order to estimate precision given a sample size of 30. The lower confidence level will be used to inform recruitment, retention, and adherence planning in the future RCT (Table 2). **Hypothesis**

Generation: Differences between baseline and post-treatment secondary outcome measures will be used to generate hypotheses for a larger RCT targeting PTSD symptoms (with a particular focus on hyperarousal) as a primary outcome, and anxiety, depression, and sleep as secondary outcomes, in order to evaluate taVNS efficacy. Estimates and variances at each time point will be used to calculate effect sizes to plan the larger RCT. We will be cautious about using our findings from this pilot study to inform underlying assumptions regarding the true magnitude of the effect of taVNS. This is because effect sizes observed in pilot studies are crude, due to the small sample size, and may not be indicative of the true difference in the larger population. We will also use results to generate hypotheses regarding potential mechanisms of action including the various inflammatory, neural, and cardiovascular changes that correlate with treatment outcomes. We will explore whether the impact of taVNS on PTSD symptoms is mediated by biologic measures of physiological reactivity and inflammatory markers (Table 1).

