9 STATISTICAL CONSIDERATIONS

9.1 STATISTICAL ENDPOINTS AND HYPOTHESES

Our primary outcome measures are expected to be 75% for recruitment, 90% for retention, and 80% for adherence. We calculated two-sided 95% confidence intervals for one proportion using the Clopper-Pearson method with scenarios varying the expected percent (0.70 and 0.95) in order to estimate precision given a sample size of 30. The lower confidence level will be used to inform recruitment, retention, and adherence planning in the future RCT.

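### The feasibility definition uses 70% retention and 70% adherence, but Table 1 lists unlabelled goals of 90% and 80% for the same primary measures, and its adherence line contains an hours total that does not fit the schedule

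*Protocol*

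**What the plan says.** The definition of feasibility appears three times in the protocol: in the synopsis (1.1), in section 3 and in section 8.1. Each time it requires 75% recruitment together with 70% adherence and 70% retention. The synopsis wording is "as well as to show adherence to the intervention and retention rates of 70% each"; section 8.1 says "recruit 75% of eligible, approached, participants and to demonstrate intervention adherence and retention rates of 70% each (Table 1"), with Table 1 as the reference.

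Table 1 (section 6.1.1) lists the primary feasibility outcomes with a goal, in percent, beside each:

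- The entry for retention is "participants who complete baseline and 8-wk measures (both survey and biological measures) (goal = 90", in percent.
- For recruitment the goal is 75% of eligible responders consented, which agrees with the definition.
- The entry for adherence is "participants who used taVNS 15 min/day once a day for 8 weeks (21 hours total) (goal=80", in percent.

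The precision text in 8.1 and section 9.1 repeat the Table 1 figures as expectations. Section 9.1 reads: "Our primary outcome measures are expected to be 75% for recruitment, 90% for retention, and 80% for adherence". It does not mention 70%.

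Two related lines do not fit the 8-week design. The retention definition in 9.3.1 refers to 6-week measures, and the inflammatory-marker line of Table 1 places the follow-up blood draw at 6 weeks. The only follow-up visit described is at 8 weeks.

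**The concern.** The pilot exists to decide whether a larger trial is feasible, so the mark that decides this should appear once, or appear the same way everywhere. A reader who follows the reference from 8.1 to Table 1 finds higher figures for two of the three measures. A reader who starts from section 9.1 meets only the higher figures. Because recruitment is 75% in both places, Table 1 looks like the place where the thresholds are kept.

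What is at stake is the feasible or not-feasible statement. Results between the two marks would satisfy the definition and fall short of the table, and two reports of the same data could word the primary conclusion differently. The adherence measure has a further problem: its Table 1 line states a total dose that its own schedule does not produce, so it is unclear who counts as adherent whichever percentage applies.

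**Working it through.** **Inputs.** N = 30 (section 9.3.1). Definition: 70% retention and 70% adherence (1.1, 3, 8.1). Table 1 goals: 90% and 80% (6.1.1). Expected rates: 90% and 80% (8.1, 9.1). Schedule: 15 minutes once a day for 8 weeks (6.1.1, 9.3.1).

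**The plan's own figures.** Exact Clopper-Pearson 95% limits with x = 30p reproduce all six rows of Table 2 in section 9.2. For example, 0.70 gives 0.506 to 0.853, 0.80 gives 0.614 to 0.923, and 0.90 gives 0.735 to 0.979. The precision table is correct.

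**Counts needed out of 30.**

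| Measure | Definition | Table 1 goal | Meets definition, misses goal |
|---|---|---|---|
| Retention | 0.70 × 30 = 21 | 0.90 × 30 = 27 | 21 to 26 |
| Adherence | 0.70 × 30 = 21 | 0.80 × 30 = 24 | 21 to 23 |

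**Chance of landing between the marks if the expected rates are true** (exact binomial, X ~ Bin(30, p)).

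- Retention, p = 0.90: P(X ≥ 21) = 0.9995 and P(X ≥ 27) = 0.6474. The difference, P(21 ≤ X ≤ 26), is 0.352.
- Adherence, p = 0.80: P(X ≥ 21) = 0.9389 and P(X ≥ 24) = 0.6070. The difference, P(21 ≤ X ≤ 23), is 0.332.

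**Both measures together, treating each set as a pass rule.** The documents do not give the dependence between the measures, so two assumptions bracket it.

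- Independent: 0.9995 × 0.9389 = 0.938 under 70/70, and 0.6474 × 0.6070 = 0.393 under 90/80. Difference 0.55.
- Adherent participants a subset of those retained (adherent given R retained ~ Bin(R, 0.8/0.9)): 0.939 against 0.505. Difference 0.43.

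**With recruitment included.** Taking 40 eligible people from 5.5 and a true rate of 75%, P(at least 30 of 40) = 0.584. If this is independent of the other measures, the differences become 0.584 × 0.5455 = 0.32 and 0.584 × 0.4342 = 0.25.

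**Sensitivity, retention and adherence only** (subset to independent). At assumed true rates of 95% and 85% the difference is 0.17 to 0.19; at 85% and 80% it is 0.63 to 0.74.

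**Adherence dose.** 8 weeks is 56 days, and 56 × 15 min = 840 min = 14 hours. The stated 21 hours is 1,260 min, or 84 sessions, which is 84/56 = 1.5 sessions a day over 8 weeks. Two sessions a day would give 28 hours. The usage descriptions in 10.1.6 mention one to two sessions a day in one place and two in another, and 10.1.8.1 says two, against one a day in 6.1.1 and 9.3.1.

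**The case against.** The strongest reply is that a deciding rule does exist. Only the 70/70 set is called the definition, three times over, and 8.1 and 9.1 call 90% and 80% expected values. A minimum and a higher goal can coexist. Table 1's other recruitment goals behave like planning figures: 33%, 66% and 75% match the funnel in 5.5, where "we expect that 66% (n=40) will meet criteria for PTSD as per the CAPS" and "we expect that at least 75% (n=30) will agree to continue with study participation". Another goal, that all of the intervention group exceed a satisfaction score, reads as an aspiration. The reference to Table 1 may simply point to the list of measures, as it does after the acceptability items in 8.1.

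Most of this stands. A reader might infer that the protocol has no feasibility rule at all; the repeated definition rules that out. A reader might also infer that the team could choose the more favourable verdict afterwards. That is not supported either: 70/70 is the more lenient set on both measures and is already the written definition, so moving to 90/80 could only make the verdict less favourable. Nor are the probabilities of 0.17 to 0.74 error rates. An expected value used as a cut-off is often missed by chance, and these figures show how far apart a floor and an expectation lie.

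What the reply does not remove is that the floor-and-target reading has to be inferred. Table 1 sets its goals under the primary-outcome heading without that label, section 9.1 omits the thresholds, and the 21-hour total and 6-week references remain wrong on any reading.

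**Conclusion.** The point holds as an inconsistency in how the primary endpoint's thresholds are presented, worth correcting before results are known. The best reading is that 70% retention and 70% adherence, with 75% recruitment, decide feasibility and that 90% and 80% are expectations, but the protocol leaves the reader to work this out. The consequence is limited to retention of 21 to 26 or adherence of 21 to 23 out of 30, where the definition and the Table 1 goal part. Each range has a chance of about one in three if the expected rates are true. This assumes that all 30 participants form the denominator for both measures; the joint figures also rest on the assumed dependence.

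The described estimates and their 95% intervals are the same under either set, and the sample size and Table 2 are sound. The risk is a disputed or inconsistently reported verdict, not a biased result. The adherence threshold cannot be applied cleanly until the 21-hour figure is corrected.

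**What to change.** Before results are known:

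1. State in 8.1 and 9.1 that 70% retention and 70% adherence (at least 21 of 30 each), with 75% recruitment, are the deciding thresholds. The synopsis and section 3 already give these percentages.
2. Relabel the 90% and 80% in Table 1 as expected or target values.
3. In the Table 1 adherence line, change 21 hours to 14 hours (15 min × 56 days). Bring the session counts in 10.1.6 and 10.1.8.1 into line with once-daily use.
4. Change 6 weeks to 8 weeks in the 9.3.1 retention definition and in the Table 1 blood-draw line.

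The cost is a wording amendment. No participants, visits or procedures are added, and the sample size and Table 2 stay as they are.

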8.2 SAFETY ASSESSMENTS

Co-primary Safety Endpoints: The primary safety endpoint is the occurrence of any discomfort or harm in healthy, able-bodied participants during taVNS protocol.

Secondary Study Endpoint: The efficacy and specificity of taVNS will be determined by the effect of noninvasive stimulation on the calculated index. This study will explore the changes in the ANS and its branches from taVNS, as well as the stimulation parameters to achieve significant results.

There are no anticipated problems that are associated with this non-invasive study. In the unlikely event that a participant is harmed from being in the study, medical care and treatment will be provided by Northwell Health. However, the participant will be responsible for the costs of any medical treatment, directly or through medical insurance and/or other forms of medical coverage.

8.3 ADVERSE EVENTS AND SERIOUS ADVERSE EVENTS

8.3.1 DEFINITION OF ADVERSE EVENTS (AE)

An adverse event is any untoward medical occurrence regardless of causality assessment. An adverse event can be an unfavorable and unintended sign, symptom, syndrome, or disease associated with or occurring during an investigation, whether or not considered related to the investigation.

8.3.2 DEFINITION OF SERIOUS ADVERSE EVENTS (SAE)

A serious adverse event is any undesirable experience or untoward medical occurrence associated with an investigation that:

- Led to death
- Led the health of a subject to diminish such that it resulted in:
 - Life threatening illness or injury
 - Required inpatient hospitalization or prolongation of existing hospitalization
 - Resulted in a permanent impairment of a body structure or a body function
 - Resulted in a congenital anomaly or birth defect
 - Resulted in medical or surgical procedure to prevent permanent impairment or damage to a body structure or function

8.3.3 CLASSIFICATION OF AN ADVERSE EVENT

8.3.3.1 SEVERITY OF EVENT

Protocol Number: 21-0640

February 1, 2022

For consistency of labeling and categorizing adverse events, the Common Terminology Criteria for Adverse Events (CTCAE v4.03) will be used on this study. The grading will be performed as follows:

- Grade 1 = mild adverse event.
- Grade 2 = moderate adverse event.
- Grade 3 = severe and undesirable adverse event.
- Grade 4 = life-threatening or disabling adverse event.
- Grade 5 = death.

The identification of an adverse event may be from observation, participant notification, clinical assessment, or results from tests.

- **Mild** – Events that require minimal or no treatment and do not interfere with the participant's daily activities.
- **Moderate** – Events that result in a low level of inconvenience or concern. Moderate events may cause some interference with functioning.
- **Severe** – Events that interrupt a participant's usual daily activity and may require treatment. Severe events are usually potentially life-threatening or incapacitating.
- **Life-threatening** – Events that require urgent intervention to sustain life or prevent severely debilitating condition.
- **Death** – Events that are related to death.

8.3.3.2 RELATIONSHIP TO STUDY INTERVENTION

All adverse events (AEs) will have their relationship to study intervention assessed based on temporal relationship. The degree of certainty about causality will be graded using the categories below.

- **Definitely Related** – There is clear evidence to suggest a causal relationship, and other possible contributing factors can be ruled out. The clinical event occurs in a plausible time relationship to study intervention administration and cannot be explained by concurrent disease or other drugs or chemicals.
- **Probably Related** – There is evidence to suggest a causal relationship, and the influence of other factors is unlikely. The clinical event occurs within a reasonable time after administration of the study intervention, is unlikely to be attributed to concurrent disease or other drugs or chemicals.
- **Possibly Related** – There is some evidence to suggest a causal relationship (e.g., the event occurred within a reasonable time after administration of intervention). However, other factors may have contributed to the event (e.g., the participant's clinical condition, other concomitant events).
- **Not Related** – The adverse event is completely independent of study intervention administration, and/or evidence exists that the event is definitely related to another etiology.

